5.1 PRIMARY ENDPOINT

The primary endpoint is progression-free survival (PFS) calculated as the time from randomisation until progressive disease (PD) according to RECIST or death from any cause, whichever occurs earlier. The date of PD will be based upon blinded independent assessment.

The rules to determine the PFS outcome (event or censored) along with the date of outcome are specified in [Table 5.1: 1](#). These rules will be applied to the independent assessment data prior to analysis.

In order to identify whether radiological imaging assessments are missing, a nominal time-point based on the scheduling detailed in the CTP will be assigned to each assessment according to [Table 6.7: 1](#). If a patient does not have an assessment for one of the scheduled time-points, it will count as a missed assessment. Any assessment with an overall tumour

response of Not Evaluable (NE) will be considered as a missed assessment and cannot be used as an outcome date.

Table 5.1: 1 Derivation rules for PFS

Status at time of analysis	Outcome	Date of outcome
No baseline radiological assessment and/or no post-baseline radiological assessments		
Death on or before the second planned radiological assessment	Event*	Date of death
Vital status is unknown or alive or death after second radiological assessment	Censored	Date of randomisation
With baseline and at least one post-baseline radiological assessment		
Alive and non-PD, no more than one consecutively missed radiological assessment	Censored*	Date of last radiological assessment
Alive and non-PD, two or more consecutively missed radiological assessments	Censored*	Date of last radiological assessment prior to missed radiological assessments
PD, no more than one consecutively missed radiological assessment prior to PD	Event*	Date of radiological assessment of PD
PD, two or more consecutively missed radiological assessments prior to PD	Censored*	Date of last radiological assessment prior to missed radiological assessments
Death and non-PD, no more than one consecutively missed prior radiological assessment prior to death	Event*	Date of death
Death and non-PD, two or more consecutively missed radiological assessments prior to death	Censored*	Date of last radiological assessment prior to missed radiological assessments
Initiation of subsequent anti-cancer therapy		
Subsequent anti-cancer therapy started before the outcomes flagged with a '*' above	Censored	Date of last radiological assessment before subsequent anti-cancer therapy (or date of randomisation if none exist)

* For these outcomes if initiation of subsequent anti-cancer therapy occurred prior to the outcome date then the rule for the final row of table will be used instead

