2.1.3 Secondary endpoints

- Overall survival (OS) is defined as the time from randomisation until death from

any cause.

- Disease control (DC) is defined as a best overall response of complete response (CR), partial response (PR), stable disease (SD) or Non-CR/Non-Progressive Disease (Non-CR/Non-PD). SD and Non-CR/Non-PD must have a minimum duration of 24 weeks from randomisation. Best overall response is defined according to RECIST version 1.1 and will consider all tumour assessments from randomisation until the earliest of disease progression, death or last evaluable tumour assessment before start of subsequent anti- cancer therapy, loss to follow-up or withdrawal of consent.
- Duration of DC is defined as the time from randomisation until the earliest of disease progression or death, among patients with DC.
- Objective response (OR) is defined as a best overall response of CR or PR. Best overall response is defined according to RECIST version 1.1 and will consider all tumour assessments from randomisation until the earliest of disease progression, death or last evaluable tumour assessment before start of subsequent anti-cancer therapy, loss to follow-up or withdrawal of consent.
- Time to pain progression or intensification of pain palliation defined as the time from randomisation until the earliest of a clinically significant increase in pain (≥ 2 -point increase from baseline in the Brief Pain Inventory– Short Form [BPI-SF] Item 3) without a decrease in analgesics use, or intensification in pain palliation (≥ 2 -point increase in the 8-point Analgesic Quantification Algorithm [AQA]), or death.

** Note if the trial is expanded the secondary endpoint of OS is included in the statistical testing strategy in a hierarchical manner subsequent to significance being observed in the primary endpoint, for further details refer to [Section 7.2](#).*

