7.3.2 Secondary endpoint analyses Overall survival

OS will be analysed using the same statistical methods as for PFS. OS will be included in the confirmatory strategy in a hierarchical manner if the trial is expanded into a Phase III trial.

OS is defined as the time from randomisation until death from any cause. For patients with ‘event’ as an outcome for OS:

- OS [days] = date of outcome – date of randomisation + 1.

For patients with ‘censored’ as an outcome for OS:

- OS (censored) [days] = date of outcome – date of randomisation + 1

The censoring rules for OS (i.e. outcome and date of outcome) are given in [Table 7.5: 2](#). The time frame for the primary assessment of OS will be from randomisation until the earliest of death or the time point of the primary OS analysis (refer to [Section 7.3](#)).

In addition to the main analysis the following analyses may be performed to examine the pattern of time to death for consistency with the PFS results, while accounting for the extent and influence of post-progression intervention if deemed necessary:

- describe the cumulative proportion of deaths at each scheduled tumour assessment time point
- tabulate the specific anti-cancer treatments after progression
- describe the effect of additional anti-cancer treatment, by separating patients into the following sub-groups:
 - those not eligible for additional treatment
 - patients who did not progress

- patients who died within one month of progression
- those eligible for additional treatment (i.e. those who have progressed and not died in the first month after progression)
 - did not take additional treatment
 - did take additional treatment

Disease control

DC will be analysed in terms of DC rate (DCR), defined as the proportion of patients with best overall response of CR, PR, SD or Non-CR/Non-PD. The DCR will be calculated for each treatment group, overall and within each level of the stratification factors. Proportions will be presented with 95% CIs. A logistic regression model adjusting for the stratification factors where appropriate will be used to compare the DCR between the two treatment groups.

For the primary assessment of DC, tumour imaging will be performed every 8 weeks up to week 80 and every 12 weeks thereafter until the earliest of disease progression, death or last evaluable tumour assessment before the start of subsequent anti-cancer therapy or the time point of the primary PFS analysis (refer to [Section 7.3](#)).

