A best overall response of SD or Non-CR/Non-PD must have a minimum duration of 24 weeks from the date of randomisation.

Duration of disease control

For all patients with DC the duration of DC is defined as the time from randomisation until the earliest of disease progression or death.

For patients with disease progression or death:

- Duration of DC [days] = date of outcome – date of randomisation + 1

For patients without disease progression or death:

- Duration of DC (censored) [days] = date of outcome – date of randomisation + 1

The censoring rules for DC (i.e. outcome and date of outcome) are described in [Table 7.5: 1](#). The time frame for the primary assessment of duration of DC will be from randomisation until the earliest of disease progression, death or the time point of the primary PFS analysis (refer to [Section 7.3](#)).

Kaplan-Meier estimates will be used to calculate median duration of DC for each treatment group.

Objective response

OR will be analysed in terms of OR rate (ORR), defined as the proportion of patients with best overall response of CR or PR. The ORR will be calculated for each treatment group, overall and within each level of the stratification factors. Proportions will be presented with 95% CIs. A logistic regression model adjusting for the stratification factors where appropriate will be used to compare the ORR between the two treatment groups.

For the primary assessment of OR, tumour imaging will be performed every 8 weeks up to week 80 and every 12 weeks thereafter until the earliest of disease progression, death or last evaluable tumour assessment before the start of subsequent anti-cancer therapy or the time point of the primary PFS analysis (refer to [Section 7.3](#)).

As per RECIST 1.1 guidance confirmation of OR is not a requirement for randomised trials.

Time to pain progression or intensification of pain palliation

Xentuzumab may delay the time to pain worsening. To investigate this, each patient's pain severity and usage of pain palliation will be assessed. Time to pain progression or intensification of pain palliation is defined as the time from randomisation until the earliest of a clinically significant increase in pain (≥ 2 -point increase from baseline in the BPI-SF Item 3) without a decrease in analgesic use, intensification in pain palliation (≥ 2 -point increase in the 8-point AQA) or death.

For patients with 'event' as an outcome for pain progression/intensification of pain palliation:

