7.5 HANDLING OF MISSING DATA

In general missing efficacy data will not be imputed and all reasonable efforts will be taken during the study to obtain such data. Patients with unknown vital status, missing tumour imaging data and missing PRO assessments will be censored for time to event analyses as detailed below.

[Table 7.5: 1](#) describes how patients will be classified for the analysis of PFS. Sensitivity analyses will examine the effect of using alternative rules.

Table 7.5: 1 Derivation rules for PFS

Situation	Outcome	Date of outcome
No baseline radiological assessment		
Death on or before the second planned radiological assessment	Event	Date of death
Alive or death after second radiological assessment	Censored	Date of randomisation
Without post-baseline radiological assessments		
Vital status is unknown or known to be alive	Censored	Date of randomisation
Death prior or on the second planned radiological assessment	Event	Date of death
Death beyond the second planned radiological assessment	Censored	Date of randomisation
With baseline and post-baseline radiological assessments BUT no other anti-cancer therapy		

Table 7.5: 1 Derivation rules for PFS (cont'd)

Alive and not progressed, no more than one consecutively missed radiological assessments	Censored	Date of last radiological assessment
Alive and not progressed, two or more consecutively missed radiological assessments	Censored	Date of last radiological assessment prior to missed radiological assessments
Progressed, zero or one missed radiological assessment prior to progression	Event	Date of radiological assessment of progression
Progressed, but two or more consecutively missed radiological assessments prior to progression	Censored	Date of last radiological assessment prior to missed assessment
Death but no progression, zero or one missed radiological assessment prior to death	Event	Date of death
Death without progression, but two or more consecutively missed radiological assessments prior to death	Censored	Date of last radiological assessment prior to missed assessments
Initiation of subsequent anti-cancer therapy		
Subsequent anti-cancer therapy started before progression or death	Censored	Date of last radiological assessment before subsequent anti-cancer therapy
No baseline and/or post-baseline imaging and subsequent-anti cancer therapy started prior to a death	Censored	Date of randomisation

For endpoints related to OR and DC the rules defined above, where applicable, will be followed.

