5.2.2 Secondary endpoints

Overall survival

Overall survival (OS) will be calculated as the time from randomisation to death from any cause. Patients without evidence of death will be censored at the date of last contact when known to be alive.

Disease control

Disease control (DC), defined as a best overall response (BOR) of complete response (CR), partial response (PR), stable disease (SD) or Non-CR/Non-PD. SD and Non-CR/Non-PD must have been observed up until at least the Week 24 tumour assessment.

BOR is defined according to RECIST based on all evaluable tumour assessments from randomisation until the earliest of PD, start of subsequent anti-cancer therapy, loss to follow-up, withdrawal of consent or death. To be aligned with the primary endpoint derivation, tumour assessments after two or more consecutively missed assessments will not be considered.

Duration of disease control

Duration of DC will be calculated as the time from randomisation until the earliest of PD (according to RECIST) or death from any cause, among patients with DC.

The outcome rules defined in [Table 5.1: 1](#) will be used for the calculation.

Objective response

Objective response (OR), defined as a BOR (as detailed for DC) of CR or PR.

Time to pain progression or intensification of pain palliation

Time to pain progression or intensification of pain palliation, defined as the time from randomisation until the earliest of:

- ≥ 2 point increase from baseline in the Brief Pain Inventory – Short Form (BPI-SF), Item 3 (worst pain), without a decrease (of ≥ 1 point) from baseline analgesics use (via the 8-point Analgesic Quantification Algorithm [AQA]), or
- ≥ 2 point increase from baseline in the AQA, or
- Death

The rules to determine outcome (event or censored) along with the date of outcome are specified in [Table 5.2.2: 1](#). These rules will be applied to the independent assessment data prior to analysis.

[figure not shown]
In order to identify whether questionnaire assessments are missing, a nominal time-point based on the scheduling detailed in the CTP will be assigned to each assessment according to [Table 6.7: 2](#). If a patient does not have an assessment for both the BPI-SF, Item 3 and the AQA score at one of the scheduled time-points, it will count as a missed assessment;

[figure not shown]

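### Two missed scans end a patient's PFS and response follow-up even when a later scan shows no progression, and the Protocol disagrees with itself on whether this applies to best overall response

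*SAP*

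**What the plan says.** **PFS.** The Protocol row reads "Alive and not progressed, two or more consecutively missed radiological assessments" (7.5, Table 7.5: 1) and the SAP row "Alive and non-PD, two or more consecutively missed radiological assessments" (5.1, Table 5.1: 1). In both, the outcome is censoring at the last scan before the missed ones. A companion SAP row, "PD, two or more consecutively missed radiological assessments prior to PD", is censored at the same date. Neither table says whether the gap must come directly before the PD or death. SAP 5.1 adds that any scan with an overall "response of Not Evaluable (NE) will be considered as a missed assessment and cannot be used as an outcome date".

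**Duration of disease control.** Protocol 7.3.2 states "The censoring rules for DC (i.e. outcome and date of outcome) are described in" Table 7.5: 1. SAP 5.2.2 points to Table 5.1: 1.

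**BOR, which drives OR and DC.** SAP 5.2.2, citing alignment with the PFS derivation, says that "tumour assessments after two or more consecutively missed assessments will not be considered". Protocol 2.1.3 says BOR "will consider all tumour assessments from randomisation until the earliest of disease progression", death, or the last evaluable scan before new therapy, loss to follow-up or withdrawal. Protocol 7.3.2 runs the DC and OR assessment "until the earliest of disease progression, death or last evaluable tumour assessment before the start of subsequent anti-cancer therapy" or the primary PFS analysis. Appendix 10.4 ends the window at progression or new treatment. None of these three has a missed-scan cut. The sentence below Table 7.5: 1, however, extends that table's rules to OR and DC so far as they apply.

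**The concern.** Two-missed censoring protects against a PD or death whose timing is unknown because nobody looked for a long time. Once an evaluable scan after the gap shows non-PD, that uncertainty has gone for everything up to that scan. A PD found later is then bounded by the scan before it, as for any other patient. The rule as written still discards the later follow-up and the later PD.

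At stake are some precision in a trial of about 40 events that, without expansion, is read from the hazard ratio and its interval in an explorative way, and the OR and DC status of a few patients, which depends on which Protocol section is followed.

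**Working it through.** **1. When the row has an effect.** If the missed scans are the patient's last, the last scan and the last scan before the missed ones are the same date, so this row and the row for at most one missed scan agree. The row changes a result only when an evaluable scan follows the gap. SAP 5.2.2 confirms this reading by dropping post-gap scans from BOR for the sake of alignment with PFS.

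**2. One patient.** SD at week 8; weeks 16 and 24 missed or NE; SD at weeks 32, 40 and 48; PD at week 56.
- PFS as written, before the PD: censored at week 8, losing 48 − 8 = 40 weeks of observed follow-up.
- PFS on the SAP 5.2.2 reading, after the PD: still censored at week 8, although the PD is located within 56 − 48 = 8 weeks. Both tables accept a PD after one missed scan, an interval of 16 weeks.
- DC under SAP 5.2.2: no, since only week 8 counts. DC under Protocol 2.1.3: yes, since SD lasts beyond 24 weeks.

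**3. The plan's own figures.** Table 7.7: 1 uses Φ(ln(threshold/HR) × √(events/4)). With 40 events and HR 0.50, Φ(ln(0.60/0.50) × √10) = Φ(0.577) = 71.8% and Φ(ln(0.75/0.50) × √10) = Φ(1.282) = 90.0%, both as stated. Exponential medians of 9.9 and 19.8 months, 80 patients accrued over 15 months and a cut at month 30 give 52.9 events without loss. With the stated 20% loss this is 0.8 × 52.9 = 42.3, consistent with about 40. No design figure is wrong.

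**4. Size of the effect.** Inputs from Protocol 7.7 and the SAP 6.7 schedule: 80 patients 1:1, HR 0.50, scans every 8 weeks to week 80 and then every 12. Assumptions: a missed/NE rate per scan of 5%, 10% or 20%, independent and unrelated to outcome; exponential drop-out of 0.0225 per month (about 20% leave without PD); all events scan-detected; unstratified Cox model with Breslow ties. Simulation of 3000 trials per rate, rule as written → censoring only when the gap directly precedes the PD:

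| | 5% | 10% | 20% |
|---|---|---|---|
| PFS events | 41.12 → 41.34 | 39.69 → 40.47 | 35.11 → 37.67 |
| Person-months | 863 → 872 | 833 → 865 | 737 → 848 |
| Median SE of log HR | 0.3246 → 0.3237 | 0.3303 → 0.3270 | 0.3532 → 0.3397 |
| 95% CI upper/lower, exp(2 × 1.96 × SE) | 3.57 → 3.56 | 3.65 → 3.60 | 3.99 → 3.79 |
| Median HR | 0.515 → 0.515 | 0.515 → 0.518 | 0.516 → 0.511 |
| Patients with week-24 DC | 52.84 → 53.18 | 51.72 → 52.98 | 47.83 → 52.61 |

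Events recovered: 0.2, 0.8 and 2.6, split xentuzumab/control 0.10/0.12, 0.36/0.42 and 1.17/1.39. The DC gains of 0.3, 1.3 and 4.8 patients are upper bounds, because a CR or PR before the gap already counts.

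**5. Second run, with clustering.** A separate 400-trial simulation with drop-out of 0.0176 per month recovered 0.3, 0.8 and 2.9 events at the same independent rates. With clustered misses:
- 10% rate, 30% chance that a miss is followed by another: events 37.7 → 39.9; DC rate 62.1% → 66.8%.
- 20% rate, 50% chance: events 28.4 → 33.2; DC rate 50.2% → 64.2%.

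Putting these event counts into the step 3 formula, the probability of an observed HR ≤ 0.60 moves by at most 1.3 points (68.7% → 70.0%).

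**6. Objective response.** If first response came at week 32, the rule loses it with probability 2p² − p³ (two consecutive misses among weeks 8, 16 and 24): 0.0049, 0.019 and 0.072. Borrowing the 12.6% response rate in Protocol 1.1, 80 × 0.126 = 10.1 responders, so about 0.05, 0.2 and 0.7 are lost.

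**The case against.** **Bone scans.** In patients with bone disease, bone scans accompany only every other CT (weeks 8, 16 and 32, not 24 and 40). If weeks 24 and 32 are missed, week 40 is CT without a scheduled bone scan, and Appendix 10.4 warns that CT or MRI alone can miss small or new lesions. Stopping at the gap is then cautious. This does not defeat the change, because missing week 32 alone already leaves no bone scan from week 16 to week 48 and the plan accepts that. It stands as a reason to flag such cases. Likewise, a nadir lost in the gap could make a later scan read as non-PD, but a single missed scan can do the same.

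**The SAP has a Protocol basis.** A reader might infer that SAP 5.2.2 contradicts the Protocol. The documents do not support that: Protocol 7.5 extends the PFS rules to OR and DC, and the SAP follows it. What remains is that 7.5 disagrees with 2.1.3, 7.3.2 and Appendix 10.4, and that SAP section 4 does not mention which side was taken.

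**NE as missed.** A reader might call this an unlisted change too. It is not: Protocol 7.5 does not define a missed assessment, and SAP section 3 describes the SAP as detailed elaboration of the Protocol.

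**Size and convention.** The PFS rule is prespecified and identical in both documents. The SAP Table 6.7: 1 windows are contiguous and at least 8 weeks wide, so two missed means no evaluable scan for about 16 weeks or more, which makes 20% per scan look high. The 12.6% response rate comes from another trial's overall population, while patients with only non-measurable bone disease are eligible here. All of this stands and keeps the point small.

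**Sensitivity analyses.** Protocol 7.5 promises alternative rules. SAP text after 7.4.1 is redacted, so a matching analysis cannot be called absent. The promise does not settle the BOR definition.

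**Conclusion.** The point holds as a minor one. Both PFS tables discard usable follow-up after a gap that a later scan has closed and, on the reading SAP 5.2.2 confirms, later well-dated PD as well. The Protocol gives two answers on whether the cut applies to BOR.

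Under independent miss rates of 5% to 20%, which are assumed because the documents give none, the cost is about 0.2 to 3 of about 40 PFS events and about 0.3 to 5 disease-control patients. It is negligible at 5% or less. Clustered misses would make it larger; the SAP's provision for COVID-19 disruption makes clustering plausible but does not show it.

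A reader might infer that the rule biases the arms or lies behind the no-added-benefit result in Protocol 1.4. Neither is supported. The simulated median HR shows no systematic shift. A single trial's HR moves by a median of less than 0.001, 0.016 and 0.035 at 5%, 10% and 20% (95th percentiles 0.03, 0.06 and 0.11). These figures assume that misses are unrelated to outcome.

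**What to change.** 1. **BOR.** Remove the post-gap restriction from SAP 5.2.2 so that OR and DC follow Protocol 2.1.3, and amend the sentence under Table 7.5: 1 to match.
2. **PFS and duration of DC.** In both tables, apply two-missed censoring only when the missed or NE scans immediately precede the PD or death. Censor alive non-PD patients at their last evaluable scan. Keep the current rule as a sensitivity analysis.
3. **Bone disease.** Flag patients whose post-gap non-PD scan was a CT without a scheduled bone scan, since that evidence is weaker.

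Protocol 1.4 reports the primary analysis complete, so the prespecified primary estimate should stay. Report the revised PFS rule and BOR as labelled supplementary analyses, and state that BOR was derived under Protocol 7.5 rather than the wording of 2.1.3.

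Cost: a few sentences in the two documents or the trial report, and minor reprogramming. No new data are needed. The downside is crediting some progression-free time on weaker bone evidence, which the flag makes visible.
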